#### **8.3.6 Change in Bone Formation (PET-MRI/PET-CT Substudy)**

To evaluate the effect of BKZ or CZP on changes in bone formation, an independent assessment of SIJ radiographs at Screening (to assess eligibility of subjects for the PET-MRI/PET-CT substudy) and PET-MRI/PET-CT scans of the entire spine and SIJ (to assess positivity and efficacy in subjects eligible for the substudy) at Baseline, Week 12 and Week 48 will be conducted.

##### **8.3.6.1 Eligibility assessment**

SIJ radiographs at Screening will be independently assessed in a blinded fashion by two reviewers. An image quality assessment will be performed, modified New York (mNY) scores

recorded and a subject's eligibility determined (subjects must be mNY-positive to be randomized into the substudy). If there is disagreement between the two primary reviewers in the assessment of eligibility, then a third reviewer will perform an adjudication based on an independent assessment of the images. The results of the adjudication of eligibility will be considered as the final assessment.

All data recorded for the eligibility assessment, including imaging date, quality of image, right and left SIJ sacroiliitis scoring and radiograph assessment (mNY-positive/negative) will be listed by treatment group for each primary reviewer and for the adjudicator (if applicable). The listing will include all subjects in the SS who were randomized into the PET-MRI/PET-CT substudy.

### **8.3.6.2 Efficacy assessment**

SIJ and spine PET-CT and PET-MRI scans will be independently assessed at each time point (Baseline, Week 12 and Week 48) in a blinded fashion by two reviewers, with an additional adjudication read by a third reviewer, if applicable. Independent reviewers will assess PET-MRI/PET-CT examinations quantitatively using VU University Medical Center (VUMC)'s in-house software (ACCURATE).

Initially, two primary readers will independently assess the images visually to identify PET-positive lesions in the SIJ and spine. The readers will dichotomously score the presence or absence (1 versus 0) of PET-positive lesions in each side of the SIJ (Left and Right) and at each of the 24 spinal levels and 4 spinal regional levels [C2-C7 (Cervical), T1-T12 (Thoracic), L1-L5 (Lumbar), Sacrum] in each of the following 8 spinal locations:

- Process spinosus
- Costo-vertebral (right)
- Costo-vertebral (left)
- Facet joint (right)
- Facet joint (left)
- Anterior vertebra
- Posterior vertebra
- Vertebra (other)

For each subject, PET-positive lesions may be identified in one or both sides of the SIJ and in one or more of the 192 possible anatomical locations (spinal location/level combinations). It is expected that only one lesion for a subject may be separated/identified in each side of the SIJ or individual anatomical location in the spine, therefore, there is a direct mapping of a subject's lesion to a SIJ side or spinal location/level.

If there is a discrepancy between the two primary readers in the presence of PET-positive lesion assessment (Yes versus No for lesions in any side of the SIJ and 1 versus 0 for lesions in any spinal location), a consensus adjudication will take place with a third reader who will also be blinded to the clinical data. This reader will make an independent assessment and the results of the adjudication will be considered as the final assessment of the presence of PET-positive lesions.

Another reader who has not been involved in the visual identification of the PET-positive lesions, either as a primary reader or an adjudicator, will then draw volumes of interest (VOIs) on the pre-identified PET-positive lesions. In the case that no PET-positive lesions have been identified for a subject, then the final review step to draw VOIs will not occur. Efficacy PET-MRI/PET-CT review will occur provided that an acceptable PET-CT or PET-MRI scan is available and that PET-positive lesions were identified on the previous scan (for the Week 12 and Week 48 visits). During the PET-positive lesion VOI review, the independent reviewer will perform a quantitative assessment in ACCURATE and record the standard uptake values of  $^{18}\text{F}$ -fluoride in VOIs, corrected for both body weight and individual integrated whole blood activity concentration (SUVauc) for each PET-positive lesion identified during the PET-positive lesion identification review.

Data from the visual identification of PET-positive lesions and the results of the quantitative VOI review (i.e. SUVauc) will be listed, for each independent reader and adjudicator (if applicable), for each anatomical location in the spine, and for each side of the SIJ, by treatment group and visit for subjects in the SS who were enrolled into the PET-MRI/PET-CT substudy.

No formal statistical modelling of the PET-MRI/PET-CT imaging data will be performed for this substudy; only summaries will be presented together with 95% CIs for mean values, as applicable.

The summaries described below based on the visual identification of PET-positive lesions will include the final assessment data, ie, if adjudication was performed, then the adjudicated data will be summarized, otherwise data from one of the primary reviewers will be summarized.

All summaries will be presented for the PET-PPS.

Since the attenuation correction and quantification is variable in PET-MRI scans, PET-MRI imaging data will be listed but will not be aggregated with the PET-CT imaging data in the summaries.

Due to the predicted sparseness of the number of PET-positive lesions in each of the individual anatomical locations of the spine, data will be pooled as follows for the purpose of some of the summaries:

- In the SIJ and spine overall (across the SIJ and all anatomical locations in the spine);
- In the SIJ overall (across both sides), and split by Left and Right side;
- In the spine overall (across all anatomical locations in the spine), and split by spinal regional level (Cervical, Thoracic, Lumbar, Sacrum), and, depending on the distribution of lesions across the spine, further by spinal levels and spinal locations in which at least 1 PET-positive lesion is identified.

An overview of the total number of PET-positive lesions identified in the spine across all subjects in each of the individual anatomical locations will be presented by visit.

The presence of PET-positive lesions identified in the SIJ and spine will be summarized by visit. The summary will include the number and percentage of subjects at each visit with any PET-positive lesions in the spine or the SIJ, in both the spine and the SIJ, in the SIJ overall (and split by Left and Right side) and in the spine overall [and split by spinal regional level (Cervical, Thoracic, Lumbar and Sacrum) and level/location, as applicable]. This summary will also

include a total count of PET-positive lesions across subjects for each of the pooled locations described above. In the spine, the incidence and the total number of lesions will only be presented for the anatomical locations in which at least 1 PET-positive lesion is identified.

The number of PET-positive lesions per subject in the SIJ and spine (overall and in pooled locations, as described above) will be calculated and summarized by visit using frequency counts and percentages, and/or descriptive statistics, as applicable. In addition, in the spine and SIJ overall, in the spine overall and in each spinal regional level, the changes in the number of PET-positive lesions per subject from Baseline to Week 12 and Week 48, and the changes from Week 12 to Week 48 will be summarized using descriptive statistics.

Bar charts summarizing the total number of PET-positive lesions identified in the SIJ and in the spine will be presented by treatment group and visit for each of the pooled locations described above.

Observed  $SUV_{auc}$  values for each lesion will be pooled across subjects and summarized by visit for each of the pooled locations, as described above. In the spine, the observed  $SUV_{auc}$  values will only be summarized for the anatomical locations in which at least 1 PET-positive lesion is identified. Descriptive statistics will be presented including 95% CIs for the mean observed  $SUV_{auc}$  values. In addition, changes and percentage changes in  $SUV_{auc}$  values between visits will be calculated for each subject's PET-positive lesion in the SIJ and spine, i.e. Week 12 - Baseline, Week 48 - Baseline and Week 48 - Week 12. These changes in  $SUV_{auc}$  values will be pooled across subjects and summarized by visit for each of the pooled locations described above. Descriptive statistics will be presented including 95% CIs for mean changes and percentage changes in  $SUV_{auc}$  values between visits.

Spaghetti plots of observed  $SUV_{auc}$  values for lesions in the SIJ and spine will be presented over time for the SIJ overall, the spine overall, and for each spinal regional level (Cervical, Thoracic, Lumbar, Sacrum) by treatment group.

In addition, percentage changes in  $SUV_{auc}$  values for lesions in the SIJ and spine will be summarized using waterfall plots. These plots will identify subjects' lesions by treatment group and will be presented by pooled location (as described above, as applicable) and for each visit comparison (Week 12 – Baseline, Week 48 – Baseline and Week 48 – Week 12).

The maximum of a subject's observed  $SUV_{auc}$  values will be calculated across the pooled locations described above. This maximum  $SUV_{auc}$  value per subject will be summarized at each visit together with changes and percentage changes from Baseline between visits. Descriptive statistics will be presented including 95% CIs for the mean and the mean changes/percentage changes in the maximum  $SUV_{auc}$  values.

The mean and 95% CI for the maximum  $SUV_{auc}$  values per subject in the SIJ and spine over scheduled time will also be presented by treatment group. The same plot will be repeated for the changes and percentage changes in the maximum  $SUV_{auc}$  value per subject with treatment group overlaid on the same plot.

In addition, percentage changes in the maximum of  $SUV_{auc}$  values per subject in the SIJ and spine will be summarized using waterfall plots. These plots will identify subjects by treatment group and will be presented for each visit comparison (Week 12 – Baseline, Week 48 – Baseline and Week 48 – Week 12).

Additional exploratory analyses may include examining the relationship between changes from Baseline in bone formation and changes from Baseline in ASDAS at Week 12 (primary efficacy variable) and Week 48, and also whether there are any differences in bone formation in clinical responders according to ASAS20 versus clinical non-responders at Weeks 12 and 48. Statistical modelling which accounts for multiple PET-positive lesions per subject may be used in these analyses.

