5.3 Imaging evaluation

In a subpopulation of AS0013, a PET-MRI or PET-CT scan of the entire spine will be performed at selected sites in approximately 25 subjects at Screening, and during the study at Week 12 and Week 48/Early Withdrawal Visit if PET-positive lesions were observed in the previous scan.

The PET-MRI or PET-CT scan should be performed after confirmation of eligibility for the study based on screening assessments. All subjects at selected sites are eligible provided that a separate Informed Consent form (ICF) for the imaging evaluation has been signed.

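### SUVauc change in the PET substudy is computed only for lesions still read as PET-positive, so resolved lesions have no change value and the mean decrease is expected to be understated

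*SAP*

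**What the plan says.** SAP section 8.3.6.2 sets out a two-stage read of the PET scans.

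- **Identification.** Scans "will be independently assessed at each time point (Baseline, Week 12 and Week 48) in a blinded fashion by two reviewers", with a third reader adjudicating disagreements. Each side of the SIJ and each spinal location is scored 1 or 0. At most one lesion is expected per location, so a lesion maps directly to a place.
- **Quantification.** A different reader "will then draw volumes of interest (VOIs) on the pre-identified PET-positive lesions" and records SUVauc "for each PET-positive lesion identified during the PET-positive lesion identification review". For subjects with no lesion: "In the case that no PET-positive lesions have been identified for a subject, then the final review step to draw VOIs will not occur". Follow-up review also requires "that PET-positive lesions were identified on the previous scan (for the Week 12 and Week 48 visits)".
- **Change.** Visit-to-visit changes and percentage changes are "calculated for each subject's PET-positive lesion in the SIJ and spine". The per-subject maximum is taken over observed SUVauc values.
- **Scanning.** Protocol section 5.3 calls for imaging at Week 12 and "Week 48/Early Withdrawal Visit if PET-positive lesions were observed in the previous scan".

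The missing-data rules in SAP section 4.2 cover the clinical scores, laboratory, PK and PD data. They do not mention SUVauc.

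**The concern.** A treatment that suppresses bone formation should turn some positive lesions negative. Under these rules such a lesion loses its follow-up measurement because it responded. What remains in the change tables and waterfall plots is the set of lesions that did not resolve.

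SUVauc change is the bone-formation variable named in Protocol section 4.1.3. Section 2.4 says that a TNF inhibitor is the comparator in order to reveal any difference in osteoblast inhibition. The total sample size was raised to at least 72 to secure at least 25 evaluable imaging subjects (SAP section 2.4). A summary that leaves out complete resolution is a poor basis for that comparison, and section 8.3.6.2 plans no formal modelling of the imaging data that could correct it.

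**Working it through.** The plan states no power, effect size or SD for the PET data, so there is no figure to reproduce. The mechanism comes from the text; the size can only be illustrated.

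**1. Tracing the rule**

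| Case | Week 12 SUVauc | Lesion change | Change in maximum | Week 48 scan |
|---|---|---|---|---|
| Positive at Baseline and Week 12 | yes | yes | yes | yes |
| One lesion resolves, another persists | only the persisting one | only the persisting one | yes, over observed lesions | yes |
| All lesions resolve, none new | none | none | none | no |
| New lesion at Week 12 | yes | none (no Baseline value) | enters the maximum | yes |

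**2. Threshold model A (all inputs assumed).** Baseline uptake relative to the positivity threshold is lognormal with median m and log-SD 0.3, truncated above 1. The log change has mean ln 0.7 in the better arm and ln 0.9 in the other, with SD 0.25. Over all lesions the mean change is 0.7 × exp(0.25²/2) − 1 = −27.8% and 0.9 × exp(0.25²/2) − 1 = −7.1%, a difference of −20.6 points before rounding. By simulation, keeping only lesions still above threshold:

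| m | Better arm (dropped) | Other arm (dropped) | Difference | Shrinkage |
|---|---|---|---|---|
| 1.3 | −17.0% (51%) | −0.5% (23%) | −16.5 | 1 − 16.5/20.6 = 20% |
| 2.0 | −24.1% (19%) | −5.4% (6%) | −18.7 | 1 − 18.7/20.6 = 9% |
| 3.0 | −27.1% (3%) | −6.9% (0.5%) | −20.2 | 1 − 20.2/20.6 = 2% |

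**3. Threshold model B (all inputs assumed).** Log uptake is normal with log-SD 0.5, and the threshold is the median of the candidate locations. Visit-to-visit correlation is r, and uptake falls at follow-up by the stated number of SDs (CZP, bimekizumab).

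| Shifts | r | Difference, all Baseline lesions | Still positive only | Shrinkage |
|---|---|---|---|---|
| 0, 0.5 | 0.7 | −21.1 | −16.4 | 22% |
| 0, 0.5 | 0.9 | −21.8 | −19.1 | 12% |
| 0, 1.0 | 0.7 | −37.4 | −29.2 | 22% |
| 0, 1.0 | 0.9 | −38.7 | −35.3 | 9% |
| 0.25, 0.75 | 0.7 | −18.6 | −14.4 | 23% |
| 0.5, 1.5 | 0.9 | −30.2 | −29.7 | 2% |

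With no treatment shift and r = 0.7, a mean change of −5.1% over all lesions becomes +5.4% among those still positive: an apparent worsening produced by selection alone. With shifts 0 and 1.0, between 37% and 55% of bimekizumab subjects have no change in maximum. The between-arm difference in that measure goes from −42.0 to −33.6 points (3 locations, r = 0.7) or from −41.0 to −38.6 (6 locations, r = 0.9).

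**4. Direction between arms.** Suppose resolved lesions change by −60%, and persisting ones by −5% (CZP) or −10% (bimekizumab), so the persisting-only difference is always −5 points. These inputs are arbitrary and show direction only.

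- 10% against 30% resolve: (0.3 × −60 + 0.7 × −10) − (0.1 × −60 + 0.9 × −5) = −25.0 + 10.5 = −14.5. The plan understates.
- 10% in each arm: −15.0 + 10.5 = −4.5. The plan slightly overstates.
- 30% against 10%: −15.0 + 21.5 = +6.5. The plan shows the wrong sign.

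**The case against.** Several things count against a stronger reading.

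- **Resolution is not hidden.** A reader might infer that responders vanish from the substudy. They do not. Section 8.3.6.2 also tabulates lesion presence, lesions per subject and change in lesion number, and lists reads by location. A subject with an evaluable negative Week 12 scan stays in the PET-PPS, and under SAP section 3.1 percentages default to the analysis-set denominator. This stands. Counts do not measure uptake, however, and the Week 48 mean changes still lose subjects who were negative at Week 12.
- **New lesions are not lost.** They enter the observed SUVauc, the per-subject maximum and the counts, and miss only the lesion-level change. This stands.
- **Shrinkage between arms is not automatic.** Step 4 shows that it needs more frequent or deeper resolution in the better arm. This stands, although such a differential is what the comparison is looking for.
- **The bias may be small against the noise.** In model A the shrinkage is 0.4 to 4.1 points. With 17 and 8 subjects (25 at 2:1) and one lesion each, the SDs are 18.3 and 23.6 points and the SE is √(18.3²/17 + 23.6²/8) ≈ 9.5 points; with three independent lesions each it is about 5.5. This is fair for the contrast. The within-arm shift can be larger (27.8 − 17.0 = 10.8 points at m = 1.3).
- **Locations might be carried forward in practice.** The reference to lesions identified beforehand does not expressly exclude this. Neither document says that it is done, and re-reading at each visit with a change in lesion count points the other way. If carry-forward is intended, the SAP should say so.

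**Conclusion.** The concern holds for the lesion-level and maximum SUVauc change summaries and the related plots. They condition on being read positive at follow-up, and no rule supplies a value for a resolved lesion or for a subject whose lesions all resolve.

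The within-arm decrease is expected to be understated, assuming that resolved lesions fell more than persisting ones. The between-arm difference is understated only if resolution is more frequent or deeper in the better arm. The documents do not allow the size to be computed. The threshold models put the shrinkage of the between-arm difference at about 2% to 23%, and other assumptions would give other figures.

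A reader might infer that the substudy cannot show resolution, that worsening is lost as well, or that the trial's conclusion is at risk. The documents support none of these: the count summaries and the maximum retain that information at Week 12, bone formation is exploratory, and the primary ASDAS analysis is untouched. The change is worth making because it is cheap and because SUVauc is the variable by which the protocol defines bone formation.

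**What to change.** Amend SAP section 8.3.6.2 as follows.

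- The existing VOI reader records SUVauc on every acquired follow-up scan at each Baseline-positive location, whether or not it is still read as positive. The location is carried over from the Baseline scan, using the one-lesion-per-location mapping already in the section.
- Lesion-level change and percentage change are based on all Baseline-positive locations.
- The per-subject maximum at each visit is taken over those locations plus any new lesions. Restricting it to Baseline-positive sites would drop new lesions that it now includes.
- The numbers of resolved and new lesions appear beside each change table.
- The Week 48 change summaries state how many subjects were PET-negative at Week 12 and not rescanned. Their Week 48 SUVauc remains unknown, and this makes the gap visible.

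The cost is SAP wording and some extra VOI time on scans already acquired, with no added scan, visit or reader. Carrying locations forward from Baseline does not require earlier readings to be reopened. The one drawback is that a VOI is harder to delineate where the lesion has resolved.

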
AS0013, the current subject-blind and investigator-blind study has been designed to evaluate the efficacy and safety of bimekizumab in a clinical setting in subjects with AS. The features of bone lesions are both erosive and neo-apositive and it is not clear if the inflammatory and erosive process precedes the new formation of bone. 18F-fluoride positron-emission tomography – computed tomography (PET-CT) or 18F-fluoride positron-emission tomography – magnetic resonance imaging (PET-MRI) will be used to investigate the effects of bimekizumab on the

process of osteoproliferation as determined by the inhibition of osteoblast activity. Based on data showing that TNF α blockers have limited effect on osteoblast metabolism, the current study uses a TNF α inhibitor to show a potential differential inhibition of osteoblast activity between bimekizumab and CZP.

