3.3 Other exploratory objectives

The other exploratory objectives of the study are as follows:

- To evaluate the effect of bimekizumab or CZP on changes in bone formation
- To assess the PK and immunogenicity of bimekizumab
- To assess additional biomarker, clinical, and imaging data as available
- To assess the efficacy and safety of bimekizumab or CZP during the Treatment Extension Period

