5.9 Rationale for study design and selection of dose

AS0013 is a Phase 2a, multicenter, randomized, subject-blind and investigator-blind study to evaluate the efficacy and safety of bimekizumab and CZP in adult subjects with active AS. AS0013 includes a 12-week Treatment Period, a 36-week Treatment Extension Period, and a 20-week SFU Period. Rationales for the study design, selected population, and bimekizumab doses are provided below.

Study design

AS0013 was designed to evaluate the efficacy, safety and the process of osteoproliferation using PET imaging techniques at Screening and after 12 and 48 weeks of treatment. The scientific rationale suggesting a role for IL-17A treatment in bone formation as compared to TNF α treatment is provided in detail in [Section 2.4](#).

While the primary evaluation will be conducted after 12 weeks, a 36-week Treatment Extension Period has been added in order to maintain the treatment blind after subjects have reached Week 12 (ie, the evaluation of the primary efficacy variable) and to allow continued access to IMP for subjects responding to treatment. This extension also allows further evaluation of the inhibition of the osteoproliferative effect of bimekizumab and CZP at Week 48 and to compare this to Baseline and Week 12.

Population

AS0013 was designed to evaluate the potential benefit of bimekizumab to prevent bone formation in subjects at risk of new bone formation (disease progression) and comparing the outcome to treatment with CZP. Inclusion criteria will ensure that all subjects have active AS. Some exclusion criteria are intended to eliminate subjects who may present an unacceptable safety risk were they to participate in this investigational study program. Active AS is defined by a BASDAI score ≥ 4 and a spinal pain score ≥ 4 (from BASDAI Question 2). The full list of inclusion and exclusion criteria is provided in [Section 6](#).

Dose selection

The following dose regimens of bimekizumab and CZP will be evaluated during the Treatment Period:

- Bimekizumab 160mg sc Q2W from Week 0 through Week 10
- CZP 400mg sc Q2W at Weeks 0, 2, and 4 (loading dose) followed by CZP 200mg sc Q2W in Weeks 6 to 10.

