Note that a clarification regarding the sample size for this study was provided in protocol amendment 3. As indicated above, the planned sample size of at least 60 subjects provides sufficient power to detect meaningful treatment differences in the primary efficacy variable whilst also providing at least 25 subjects for the PET-MRI or PET-CT substudy. However, due to complexities in the initiation of sites capable of performing PET-MRI or PET-CT scans, more than the planned 35 non-PET-MRI/CT substudy subjects were screened and randomized before it was possible to close enrolment at the sites not participating in the substudy. Owing to the novelty of the PET-MRI/CT outcomes within this disease area, it is considered important to ensure at least 25 evaluable subjects are included in the assessment of this exploratory objective to maximize the possibility of identifying the salient factors or variables that might differ between the treatment groups and, therefore, the total sample size is increased to at least 72 subjects. This sample size increase will not negatively impact the power to detect a difference in the primary efficacy variable at Week 12 (ie, it will remain >80%), but will ensure that the target number of subjects are included in the exploratory analysis of changes in bone formation at Week 12 and Week 48. Since the analyses of PET-MRI/CT data are exploratory and treatment effect sizes are unknown, formal power calculations were not performed. Clinical expertise does, however, indicate that a sample size of at least 25 subjects in the substudy will characterize broad differences between treatment groups.

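### The PET substudy is meant to characterise BKZ versus CZP differences in bone formation, but no planned output estimates that difference; one exploratory estimate with a CI would close the gap cheaply

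*SAP*

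**What the plan says.** Three places give the substudy a comparative purpose. Protocol 2.4 says a TNF inhibitor is used "to show a potential differential inhibition of osteoblast activity between bimekizumab and CZP". Protocol 5.9, under Population, describes evaluating prevention of bone formation and "comparing the outcome to treatment with CZP". SAP 2.4, explaining the increase to at least 72 subjects, states: "Clinical expertise does, however, indicate that a sample size of at least 25 subjects in the substudy will characterize broad differences between treatment groups".

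The formal objective is more neutral. Protocol 3.3 lists it as exploratory: "To evaluate the effect of bimekizumab or CZP on changes in bone formation". SAP 2.4 is open about the lack of power: "Since the analyses of PET-MRI/CT data are exploratory and treatment effect sizes are unknown, formal power calculations were not performed".

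On analysis, SAP 8.3.6.2 states: "No formal statistical modelling of the PET-MRI/PET-CT imaging data will be performed for this substudy; only summaries will be presented together with 95% CIs". It then plans lesion counts, changes in the number of lesions per subject, SUVauc summaries, and bar, spaghetti, waterfall and mean plots, some with the arms overlaid. For the per-subject maximum the text reads: "Descriptive statistics will be presented including 95% CIs for the mean and the mean changes/percentage changes in the maximum" SUVauc value. The optional exploratory analyses at the end of the section concern the relation to ASDAS and ASAS20 responders versus non-responders. Nowhere is a BKZ versus CZP difference, or an interval for one, defined for SUVauc or for lesion number.

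**The concern.** A randomised comparator was included partly for this question, yet the planned output stops one step short of using the randomisation. A within-arm change contains everything common to both arms, including regression to the mean, since lesions enter the analysis by being PET-positive. Only the between-arm difference removes that shared part.

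Because the SAP prints an interval for each arm, a reader looking for a differential effect may ask which interval excludes zero, or whether the two overlap. Neither is a sound comparison. With 2:1 allocation the first tends to favour BKZ, whose interval is narrower; the second is insensitive. At stake is how an exploratory result is interpreted, and nothing beyond that.

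**Working it through.** **The plan's own figure.** The PET substudy has no stated power or precision. The only power figure is for ASDAS (Protocol 15.12, SAP 2.4): at least 80% with 60 subjects at 2:1, difference 0.89, SD 1.17, correlation 0.35. Residual SD = 1.17 x sqrt(1 - 0.35^2) = 1.096; standard error = 1.096 x sqrt(1/20 + 1/40) = 0.300; ratio = 0.89/0.300 = 2.97. Two-sided 5% power is 84% (83% with the t distribution). The claim is reproduced, so the issue is confined to the PET data.

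**Inputs for the PET check.** At least 25 subjects (SAP 2.4) and 2:1 allocation (Protocol 15.12). Assumptions: 17 BKZ and 8 CZP evaluable, normally distributed per-subject change, equal SD. The documents give no SD for SUVauc, so results are in SD units.

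**95% half-widths, t x sqrt(1/n), with SD = 1.**
- BKZ: 2.120/sqrt(17) = 0.51
- CZP: 2.365/sqrt(8) = 0.84
- Difference: 2.069 x sqrt(1/17 + 1/8) = 0.89 (0.86 at 16 v 9; 1.18 at 10 v 5)

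**Reading by which interval excludes zero.** Give both arms the same true change d. Let A and B be the probabilities that the BKZ and CZP intervals exclude zero, from the noncentral t with n - 1 degrees of freedom and noncentrality d x sqrt(n). The arms are independent, so P(BKZ only) = A(1 - B) and P(CZP only) = B(1 - A).

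| d (SD) | A | B | BKZ only | CZP only |
|---|---|---|---|---|
| 0 | 0.05 | 0.05 | 5% | 5% |
| 0.3 | 0.21 | 0.11 | 19% | 9% |
| 0.5 | 0.49 | 0.23 | 38% | 12% |
| 0.6 | 0.64 | 0.31 | 44% | 11% |
| 0.7 | 0.77 | 0.40 | 46% | 9% |
| 0.8 | 0.87 | 0.50 | 44% | 6% |
| 1.0 | 0.97 | 0.68 | 31% | 2% |
| 1.5 | 1.00 | 0.95 | 5% | 0% |

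A 95% CI for the difference wrongly excludes zero in 5% at every d, about 2.5% in each direction. With 10 v 5, BKZ-only is 25% at 0.5 SD and 48% at 1.0 SD.

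**Reading by overlap.** By simulation (200,000 trials, 17 v 8), the arm intervals fail to overlap in 45% of trials at a true difference of 1.25 SD and in 26% at 1.0 SD. A CI for the difference excludes zero in 80% and 61%. The difference detectable with 80% power is about 1.25 SD.

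**What can be measured after Baseline.** Under SAP 8.3.6.2 no volume of interest is drawn when no lesion is identified, so a subject whose lesions all resolve has a lesion count of zero but no SUVauc. Under Protocol 5.3 each follow-up scan requires lesions on the previous one. For Week 12 that condition is the pre-treatment scan. For Week 48 it is the Week 12 scan, which is post-randomisation.

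**The case against.** The descriptive plan is deliberate. The rationale for Protocol Amendment 3 says the PET endpoints, their distribution and the expected difference were too poorly understood to predefine analyses, and SAP 3.1 treats all other efficacy variables descriptively. The objective names either drug, Protocol 2.4 speaks only of a potential difference, and Protocol 5.9 also has a within-arm aim: comparing Week 48 with Baseline and Week 12. All of this stands, and it rules out calling the omission an error.

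A reader might infer that the SAP leaves nothing but arm-wise means to go on, or that a shared change would be hidden. The documents do not support that. Counts, changes in lesion number and overlaid plots are planned, and SAP 3.1 requires n, mean and SD by treatment, so an unadjusted difference in per-subject measures could be worked out by hand. What is missing is the printed estimate and any Baseline adjustment.

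A reader might also take the 44% to 46% as an error rate of the plan. It is the error rate of a misreading that the plan does not prescribe; no PET success criterion exists. It also depends on the size of the shared change, as the table shows.

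What survives is that the SAP already prints intervals, and does not print the one that matches the stated comparative purpose. Amendment 3 of the SAP cites better understanding of the data and already specifies the per-subject maximum and its change, so little more need be defined.

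**Conclusion.** The gap is real and small. The documents say the substudy should characterise differences between the groups, and no planned output estimates one. Adding the estimate is a worthwhile, inexpensive improvement to an exploratory and unpowered analysis. It would be going too far to conclude that any trial result is compromised: study success is defined on ASDAS alone, and that analysis does compare the arms.

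The sizes rest on 17 v 8 evaluable subjects, normality, equal SD and a shared true change, none of which the documents fix. The evaluable number in the summaries may well be lower, because SAP 8.3.6.2 lists PET-MRI data without aggregating them with PET-CT. At any plausible size the difference will be imprecise, and a clean randomised contrast is available only at Week 12.

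**What to change.** In SAP 8.3.6.2 keep all planned summaries and add, for PET-CT subjects of the PET-PPS at Week 12, the CZP - BKZ difference with a 95% CI, labelled exploratory and without a p-value, for:

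- (a) the change in number of PET-positive lesions per subject, counting a lesion-free Week 12 scan as zero;
- (b) the change in per-subject maximum SUVauc, either adjusted for Baseline or as an unadjusted difference in means.

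For (b), report by arm how many subjects have no SUVauc because no lesion remained, and say that the contrast is conditional on a measurable lesion. Otherwise the subjects with complete resolution drop out unseen, possibly unequally by arm. Both measures are per subject, which avoids treating several lesions in one subject as independent.

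Present any Week 48 difference as descriptive only, noting its dependence on a positive post-randomisation scan. Amend the sentence that rules out formal modelling to match, and state that comments on a differential effect refer to these differences and not to which arm's interval excludes zero.

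The cost is SAP wording and a few table rows, with no new data, reads or subjects. The downside is a wide interval: about +/-0.9 SD at 25 subjects and about +/-1.2 SD if only 15 PET-CT subjects are evaluable. The report would then show openly how little a substudy of this size can resolve.
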